2.1 Background/Rationale

Full details of the background and rationale for the study are provided in Section 1 of the protocol.

2.2 Study Objectives

2.2.1 Primary objective (PO)

The primary objective of this study (**PO1**) is to determine the effect size of PRM-151 relative to placebo in change from Baseline to Week 28 in mean FVC [% predicted], pooling subjects on a stable dose of pirfenidone or nintedanib and subjects not on other treatment for IPF.

2.2.2 Secondary objectives (SO)

The secondary objectives of this study are:

- **SO1:** To determine the effect size of PRM-151 relative to placebo in change from Baseline to Week 28 in normal lung parenchyma as quantified on high-resolution CT (HRCT) imaging analysis, pooling subjects on a stable dose of pirfenidone or nintedanib with subjects not on other treatment for IPF.
- **SO2:** To determine the effect size of PRM-151 relative to placebo in change from Baseline to Week 28 in mean FVC [% predicted], separately in subjects on a stable dose of pirfenidone or nintedanib and in subjects not on other treatments for IPF.
- **SO3:** To determine the effect size of PRM-151 relative to placebo in change from Baseline to Week 28 in normal lung parenchyma as quantified on HRCT imaging analysis, separately in subjects on a stable dose of pirfenidone or nintedanib and in subjects not on other treatments for IPF.
- **SO4:** To assess the tolerability and safety of PRM-151 in subjects with IPF through Week 28.
- **SO5:** To assess the ability of PRM-151 to reduce disease-related events associated with mortality

- **SO6:** To determine the effect size of PRM-151 relative to placebo on pulmonary function in addition to mean change in FVC [% predicted]
- **SO7:** To determine the effect size of PRM-151 relative to placebo on 6 minute walk distance
- **SO8:** To determine the effect size of PRM-151 relative to placebo on DLCO.

2.2.3 Exploratory Objectives (EO)

The exploratory objectives of this study are:

- **EO1:** To evaluate the efficacy and estimate the size of effect of PRM-151 relative to placebo in change from baseline to weeks 4, 8, 12, 16, 20, and 24 in FVC [% predicted] and 6 minute walking distance, pooling subjects on a stable dose of pirfenidone or nintedanib with subjects not on other treatment for IPF and separately in subjects on a stable dose of pirfenidone or nintedanib and in subjects not on other treatments for IPF.
- **EO2:** To assess the impact of PRM-151 on disease related symptoms.
- **EO3:** To assess the impact of PRM-151, disease pathogenesis and disease progression on exploratory serum, cellular and genetic biomarkers
- **EO4:** to explore the relationship between PK and select PD parameters

2.3 Investigational plan

2.3.1 Study design and randomisation

This study is a Phase 2, randomized, double-blind, placebo controlled, pilot study designed to evaluate the efficacy and safety of PRM-151 administered through Week 24 to subjects with IPF. Subjects meeting the eligibility criteria for the study will be randomized with a 2:1 ratio to PRM-151 at a dose of 10 mg/kg every 4 weeks or placebo. The randomization will be stratified according to other treatments for IPF (with two strata: patients receiving either pirfenidone or nintedanib and patients with no other treatment for IPF, with a minimum of 25% of patients on no other treatment). Efficacy will be evaluated through pulmonary function tests (PFTs) including spirometry, Diffusion Capacity (DLCO) and Total Lung Capacity by Nitrogen washout method (TLC), quantitative imaging analysis of high resolution CT (HRCT), 6 minute walk test (6MWT), and patient reported outcomes (PROs).

Subjects will be evaluated for study eligibility during Screening within 4 weeks before enrollment and baseline assessments. Subjects who are determined to be eligible, based on screening assessments, will be enrolled in the study and randomly allocated to treatment with PRM-151 or placebo. Subjects will receive study drug treatment for at least 24 weeks.

Approximately 117 subjects will be randomly assigned on a 2:1 basis to treatment with PRM-151 or placebo, as follows:

- PRM-151 10 mg/kg IV infusion over 60 minutes days 1, 3, and 5 of week 0, then one infusion every 4 weeks

- Placebo IV infusion over 60 minutes on days 1, 3, and 5 of week 0, then one infusion every 4 weeks

After completion of study treatment through Week 24, all subjects may receive PRM-151 10 mg/kg IV infusion over 60 minutes Days 1, 3, and 5, then once every 4 weeks for up to an additional 96 weeks in an open label study extension. Dosing on Days 1, 3 and 5 will be repeated once every 24 weeks.

2.3.2 Determination of sample size

The primary objective is not to formally demonstrate the superiority of PRM-151 over placebo, but to provide a reliable estimate of the size of the effect of PRM-151 on absolute change from baseline to 28 weeks in mean FVC [% predicted], hereafter referred to as the primary endpoint. Nevertheless, the sample-size has been calculated to ensure a sufficient power to demonstrate the efficacy of PRM-151 over placebo on the primary endpoint under a set of hypotheses on effect sizes in the two groups and on the variability of the primary endpoint. The primary endpoint will be tested in a model with two types of subjects: subjects on a stable dose of pirfenidone or nintedanib, and subjects not on other treatment for IPF. The sample size calculation is based on the following assumptions:

- Primary endpoint is normally distributed.
- Homogeneity of variance, *i.e.*, the standard deviation is the same in both arms, and for both types of subjects.
- Randomization ratio PRM-151: placebo equals 2:1.
- Expected value of the primary endpoint for subjects on pirfenidone or nintedanib will be -1.5%.
- Expected value of the primary endpoint for subjects on no other treatment will be -3%.
- Expected value of the primary endpoint for subjects on PRM-151 will be $\geq 0.75\%$.
- Standard deviation of the primary endpoint is 5%.
- 75% of subjects will be on a stable dose of pirfenidone or nintedanib.
- 25% of subjects will not be on other treatment for IPF.
- Significance level (α)=0.10 two-sided.
- Desired power to demonstrate superiority is 80%.

A sample size of one hundred and two (102) evaluable subjects in total (68 PRM-151 and 34 placebo) is enough to demonstrate statistical significance at $p < 0.10$ two-sided with a power of 80% under the above assumptions. Assuming a non-evaluability rate of about 15%, 117 subjects in total (78 PRM-151 and 39 placebo) are to be enrolled. Stratified randomization will ensure a balance of PRM-151: placebo within patients on pirfenidone or nintedanib and not on any other therapy, with at least 25% of patients on no other therapy.

2.3.3 Study assessments and study plan

Efficacy Assessments

Subjects undergo testing on an every 4 week basis after randomization (occurring at weeks 4, 8, 12, 16, 20, 24 and 28) for efficacy and safety (See Figure 1). For all analysis presented in this SAP we considered W28 as the end of study date. During treatment, PFTs, 6MWT, and PROs will be evaluated on an every 4 week basis. HRCT will be performed on Day 1 as the Baseline assessment and again at the completion of treatment at Week 28. HRCT and PFTs must be done on the same day. PFTs will be reviewed centrally by reviewers blinded to treatment group and time point. This central evaluation of PFTs will be used for the primary analysis of the study.

[figure not shown]

Figure 1: Study Plan

Tolerability/Safety Assessments

Tolerability/Safety will be evaluated over the treatment period (up to week 28) from reported adverse events (AEs), scheduled physical examinations, vital signs, and clinical laboratory test results. Adverse events and concomitant medications will be assessed at all study visits. In addition, information regarding hospitalizations, emergency department visits, and unscheduled or urgent care visits to a health care provider due to a deterioration in respiratory status or symptoms will be collected at all study visits.

Schedule of events

Schedule of events	Screening ≤ 28 days	Treatment Period			Open Label Extension
		Week 0 (± 1 day)	W4, W8, W12, W16, W20, W24 (± 3 days)	W28 (± 3 days)	W28-W128 (± 3 days)
Informed Consent	x				
Demographics	x				
Past Medical History	x				
Inclusion/Exclusion	x	x			
Vital Signs	x	x	x	x	x
Physical Exam ¹	x	x		x	x
Height (cm)	x				
Weight (kg)	x	x		x	x
Prior/Concomitant Medications	x	x	x	x	x
Special list of excluded medications	x	x	x	x	x
AE/SAE Assessment		x	x	x	x
ECG & Cytokines (ONLY in the event of an IRR)		x	x	x	
Efficacy Assessment²					
Patient Reported Outcomes; K-BILD & LCQ	x	x		x	x
Pulmonary Function Tests (PFTs)	x	x		x	x
DL _{CO} ³	x	x		x	x
FRC & TLC by nitrogen washout method ⁴	x	x		x	x
HRCT (with spirometry at select sites) ⁵		x		x	x
6-minute walk test	x	x		x	x
Pregnancy test	x				
Complete Blood Count	x	x		x	x
Chemistry, BUN/creatinine	x	x		x	x
Coagulation	x	x		x	x
Status of baseline genetic characteristics ⁶		x			
Anti-pentraxin 2 antibodies (ADA), Pre-dose		x		x	x
Pentraxin-2 levels, Pre-dose		x		x	x
Exploratory laboratory assessments (optional) ⁷		x		x	x
PRM-151 dosing ⁸		x	x	x	x

¹Full physical exam at screening and an abbreviated physical exam thereafter.²PROs should be done first before PFTs and 6MWT and 6MWT should be done last after PROs and PFTs if possible. During open-label extension, subjects will have PROs, PFTs and 6MWT every 4 weeks for the first 24 weeks, then every 12 weeks³Diffusion capacity should be done on the same day as HRCT.⁴FRC & TLC by nitrogen washout method should be done on the same day as HRCT.⁵During open-labeled extension, subjects will have DLco and FRC & TLC by nitrogen washout every 12 weeks and HCRT at 1.5 years (W76) and 2.5 years (W128).⁶TLR3 L412F polymorphism, MUC5B promoter polymorphism⁷During open label extension, subjects will have optional exploratory labs at Week 128.⁸Dosing on Days 1, 3, and 5 will be repeated every 24 weeks during the extension.

3 Analysis datasets

3.1 Reasons for excluding patients from analysis datasets

3.1.1 Major protocol deviations

Major protocol deviations are defined as deviations liable to prevent or change the interpretation of the results of the primary efficacy analysis of the study. Thus, a Study Deviation Guidance Document has been prepared (Final version, dated 27 July, 2016). This guidance is not exhaustive and will be reviewed at the time of the blind review meeting.

3.1.2 Minor protocol deviations

All deviations will be reviewed and adjudicated as either major or minor during the blind review meeting before database lock and unblinding of the study drug treatment code.

3.1.3 Study treatment discontinuations - Study discontinuations

The Investigator may discontinue study drug treatment prematurely for any of the following reasons:

- Subject, Investigator, or Sponsor request
- Protocol violation
- AE
- Pregnancy
- Progression of disease that, in the opinion of the Investigator, precludes further study drug treatment
- Subject decision: a subject may withdraw consent to participate in the study at any time

Study centers that deviate significantly from the protocol without prior approval from the Sponsor and regulatory authorities may be discontinued from the study. The Investigator at each study center is responsible for ensuring the accuracy and completeness of all research records, the accountability of study drug, and the conduct of clinical and laboratory evaluations as outlined in the protocol.

All subjects are required to adhere to the protocol-specified visit schedule. If a subject misses a scheduled visit, attempts should be made to reschedule the visit within the visit windows described above. Failure to attend scheduled study visits may result in discontinuation from the study.

3.2 Primary efficacy dataset: All Treated Set (ATS)

The All Treated Set (ATS) will consist of all randomized patients having received at least one administration of the study medication. The patients will be analyzed in the treatment arm attributed by the randomization process whatever the treatment they actually received (“as randomized” analysis).

The ATS dataset will be used for the primary efficacy analyses in this trial.

3.3 Per-protocol (PP) dataset

The Per Protocol (PP) set will comprise of a subset of the ATS analysis population:

- Randomized
- treated with the IMP,
- having received the planned IMP infusions at least for the complete three first cycles
- who did not present any major protocol deviations.
- who have at least one post-cycle 3 evaluation of the primary efficacy criterion (FVC [% predicted])

The PP dataset will be used for secondary analyses of the primary efficacy criterion and for the analysis of some selected secondary efficacy criteria, as described in section 5.2.5.2.

3.4 Safety (SAF) dataset

The safety dataset is defined as all randomized subjects having received at least one dose of study treatment. In the event of subjects having received treatments that differed from those assigned according to the randomisation schedule, then the safety analyses should be conducted according to the treatment actually received (As Treated analysis) rather than according to the randomisation groups.

The SAF dataset will be used to perform the analysis of safety.

4 Endpoints for analysis

4.1 Efficacy endpoints

4.1.1 Primary efficacy endpoint

The primary efficacy endpoint for the study is the mean change from baseline in FVC [% predicted] from Baseline to Week 28. Data for FVC [% predicted] will be provided by BioMedical Systems (BMS) and analysed without any transformation or derivation. The specification on how this variable is measured and computed are provided in the BMS specification document (PRM 151-202 Analysis Plan FINAL Version 1.0 02MAY16).

4.1.2 Secondary efficacy endpoints

The secondary efficacy endpoints for the study are:

- Structural Imaging:
 - Mean change from Baseline to Week 28 in total lung volume and volume of parenchymal features on HRCT (in ml and % of total lung volume) representative of interstitial lung abnormalities (ILA) including ground glass density, reticular changes, and honeycombing, using quantitative imaging software.
 - Mean change from Baseline to Week 28 in volume of parenchymal features on HRCT (in ml and % of total lung volume) representative of normal lung (non-ILA), including normal and mild low attenuation areas, using quantitative imaging software.
 - Correlation between mean change from Baseline to Week 28 in FVC [% predicted] and mean change from Baseline to Week 28 in total lung volume and volume of parenchymal features on HRCT (in ml and % of total lung volume) representative of interstitial lung abnormalities (ILA), including ground glass density, reticular changes, and honeycombing by quantitative imaging software.
- FVC [ml and % predicted] based pulmonary function tests:
 - Proportion (%) of subjects with a decline in FVC [% predicted] of $\geq 5\%$ and $\geq 10\%$ from baseline to week 28.
 - Proportion (%) of subjects with a decline in FVC [ml] of $\geq 100\text{ml}$ and $\geq 200\text{ml}$ from baseline to week 28.
 - Proportion of subjects with an increase in FVC [% predicted] of $\geq 5\%$ and $\geq 10\%$ from baseline to week 28.
 - Proportion of subjects with an increase in FVC [ml] of $\geq 100\text{ ml}$ and $\geq 200\text{ ml}$ from baseline to week 28.
 - Proportion of subjects with stable disease by FVC [% predicted], defined as a change in FVC [% predicted] of $< 5\%$ from baseline to week 28.
 - Proportion of subjects with stable disease by FVC in ml, defined as a change in FVC of $< 100\text{ml}$ from Baseline to week 28.
- Others pulmonary function tests:

- Mean change from Baseline to Week 28 in Hb-corrected DLCO *i.e.*, diffusion capacity of carbon monoxide [% predicted].
- Other endpoints
 - Change in 6-minute walk distance [m] from baseline to week 28.

4.1.3 Exploratory efficacy endpoints

There are five types of exploratory endpoints for the study.

The first type is based on the examination of FVC [% predicted, and ml] and 6MWT [m]:

- Change from Baseline at Weeks 4, 8, 12, 16, 20, 24 and 28 for the FVC [% predicted], FVC [ml], and 6MWT distance [m].
- Change in FVC for patient subsets on either a stable dose of (i) pirfenidone or (ii) on a stable dose of nintedanib.

The second type of exploratory endpoints is based on structural imaging:

- Transitions from Baseline to Week 28 between all categories of lung features (normal, ground glass density, reticular changes, honeycombing, and mild, moderate, and severe low attenuation areas) by quantitative imaging software, will be analyzed upon further development of methodology to measure transitions.
- Correlation of transitions between categories of lung features by quantitative imaging and changes in FVC [% predicted], will be analyzed upon further development of methodology to measure transitions.
- Correlation of transitions between categories of lung features by quantitative imaging and changes in DLCO, will be analyzed upon further development of methodology to measure transitions.
- Correlation between total lung volume by nitrogen washout and total lung volume by imaging
- Correlation of changes in interstitial lung abnormalities and PROs and 6MWD
- Impact of inspiratory effort on results of HRCT quantitative imaging.
- Pulmonary Vessel Volume.
- Mean change from Baseline to Week 28 in total lung volume and volume of parenchymal features on HRCT (in ml and % of total lung volume), representative of interstitial lung abnormalities (ILA) in patients with SVC breathhold at CT scanning $\geq 90\%$ of SVC supine (comparing PRM151 vs placebo)

The third group of exploratory endpoint is based on patient reported outcomes:

- Change in Patient Reported Outcomes as measured by
 - King's Brief Interstitial Lung Disease Questionnaire (K-BILD) and
 - Leicester Cough Questionnaire (LCQ) from Baseline to Week 28.

The fourth group of exploratory endpoint is based project investigator assessed outcome :

- Acute exacerbations and time to first reported acute exacerbation

The fifth group of exploratory endpoints is related to the analysis of biomarkers:

- Changes in serum and cellular biomarkers and response according to baseline genetic characteristics: [REDACTED] analysis may be provided at a later stage than the rest of the analyses, some or all the corresponding data may not be available at the time of the database lock.

Pharmacokinetic endpoints: Pentraxin levels will be assayed at baseline, before each study dose infusion and on Week 28.

In addition to the above exploratory endpoints specified in the protocol, it has been decided to perform a retrospective collection of pre-study pulmonary function tests data and, depending on the completeness and usability of the obtained data, to provide descriptive analyses of pre-study evolution of PFT, and, if feasible, to conduct exploratory analyses on the relationship between this pre-study PFT data, and any change during the study and treatment effect.

4.2 Safety endpoints

Safety will be evaluated from reported adverse events (AEs), respiratory decline events, infusion related reactions, scheduled physical examinations, vital signs, and clinical laboratory test results and concomitant medications.

4.2.1 Adverse events

Adverse events (AE) will be coded using the latest available version of the Medical Dictionary for Regulatory Activities (MedDRA) at the start of the coding activities and will be classified by MedDRA Preferred Term (PT) and System Organ Class (SOC). A Treatment Emergent Adverse Events (TEAE) will be defined as any adverse event that occurs from the time of first study treatment dose administered to the patient until last study visit *i.e.*:

- An AE that was not present prior to receiving the first dose of IMP, or
- An AE that was present prior to receiving the first dose of IMP and increased in intensity after the first IMP administration, or
- An AE that was present prior to receiving the first dose of IMP, with no change in the intensity but with a drug relationship that became related after the first IMP administration.

Tolerability/safety will be assessed over the 28 weeks study period *i.e.*, the analysis will be based on all AEs occurring before first dose of the OLE. The analysis will focus on:

- The incidence of TEAEs
- The incidence of Treatment Emergent Serious Adverse Events (TESAEs)
- The incidence of respiratory TEAEs and TESAEs
- The proportion of subjects discontinuing study drug due to TEAEs
- All-cause mortality
- Mortality due to respiratory deterioration

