3.2. Secondary Endpoints

The secondary endpoints for the study are:

1. Structural Imaging:

- Mean change from Baseline to Week 28 in total lung volume and volume of parenchymal features on HRCT (in ml and % of total lung volume) representative of interstitial lung abnormalities (ILA), including ground glass density, reticular changes, and honeycombing, using quantitative imaging software.
- Mean change from Baseline to Week 28 in volume of parenchymal features on HRCT (in ml and % of total lung volume) representative of normal lung (non-ILA), including normal and mild low attenuation areas, using quantitative imaging software.
- Correlation between mean change from Baseline to Week 28 in FVC % predicted and mean change from Baseline to Week 28 in total lung volume and volume of parenchymal features on HRCT (in ml and % of total lung volume) representative of interstitial lung abnormalities (ILA), including ground glass density, reticular changes, and honeycombing by quantitative imaging software.

2. Safety: Tolerability/safety will be assessed over the 28-week study period by the following parameters:

- Incidence of AEs.
- Incidence of serious adverse events (SAEs).
- Incidence of respiratory AEs and SAEs.
- Proportion of subjects discontinuing study drug due to AEs.
- Change from Baseline in hematology and serum chemistries.
- All-cause mortality.
- Mortality due to respiratory deterioration.

3. Disease related events associated with mortality: The number of “respiratory decline” events over the 28-week study period as defined below:

- Unscheduled visits to a healthcare professional for respiratory status deterioration.
- Urgent care visits for respiratory status deterioration.
- Hospitalization due to a worsening or exacerbation of respiratory symptoms.

All “respiratory decline” events will be further characterized according to the definitions of IPF-related acute exacerbation, as proposed by an expert committee sponsored by the IPF Clinical Research Network and the National Heart Lung and

Blood Institute (NHLBI) (Collard, Moore et al. 2007) and applied by (Collard, Yow et al. 2013)

- Acute onset of symptoms (< 30 days in duration)
- New radiographic abnormalities (bilateral ground glass or consolidation on HRCT with no pneumothorax or pleural effusion)
- The absence of an identified infectious etiology by routine clinical practice
- Exclusion of alternative causes by routine clinical practice, including:
 - a. Left heart failure

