7.11. **Biomarker Assessments**

7.11.1. **Baseline Genetic Status**

The subject's baseline genetic status for TLR3, L412F polymorphism, and MUC5B promoter polymorphism will be collected at Baseline, if available. If the subject has not previously been tested for these genetic characteristics, a blood sample for this analysis should be drawn at baseline.

7.11.2. **Blood Sample Collection for Biomarker Assessment**

Blood samples to study exploratory serum and cellular biomarkers are to be collected pre-dose at Baseline, Week 28 and at Week 128 of the open label extension.

7.12. **Safety Measurements**

7.12.1. **Adverse Events**

An AE is any untoward medical occurrence in a subject administered a pharmaceutical product and that does not necessarily have a causal relationship with this treatment. An AE can therefore be any unfavorable and unintended sign (including an abnormal laboratory finding), symptom, or disease temporally associated with the use of study drug, whether or not related to study drug.

All AEs from signing of informed consent until last study visit will be entered in the database. For those subjects prematurely withdrawn, TEAEs will be monitored until, at least, 4 weeks from last study treatment dose or resolution of AE, whichever is earlier

7.12.1.1. **Respiratory Decline Events**

For the purposes of this study, such “respiratory decline” events are defined as follows:

- Unscheduled visits to a healthcare professional for respiratory status deterioration.
- Urgent care visits for respiratory status deterioration.
- Hospitalization due to a worsening or exacerbation of respiratory symptoms.

All “respiratory decline” events will be further characterized according to the definitions of IPF-related acute exacerbation, as proposed by an expert committee sponsored by the IPF Clinical Research Network and the National Heart Lung and Blood Institute (NHLBI) (Collard, Moore et al. 2007) and applied by (Collard, Yow et al. 2013)

- Acute onset of symptoms (< 30 days in duration)
- New radiographic abnormalities (bilateral ground glass or consolidation on HRCT with no pneumothorax or pleural effusion)
- The absence of an identified infectious etiology by routine clinical practice
- Exclusion of alternative causes by routine clinical practice including:
 - a. Left heart failure
 - b. Pulmonary embolism
 - c. Identifiable cause of acute lung injury

7.12.1.2. **Infusion related reactions**

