7.12.2. Adverse Event Assessment

All AEs from signing of informed consent until last study visit will be entered in the database, but only AEs occurred from the time of first study treatment dose administered to the subject (TEAEs) until last study visit will be analysed (see 7.12.1). This includes AEs the subject reports spontaneously, those observed by the Investigator, and those elicited by the Investigator in response to open-ended questions during scheduled study center visits.

Each AE is to be assessed by the Investigator with regard to the following categories.

Serious/Non-Serious

Adverse events that meet the criteria specified above are to be considered serious.

Relationship to Study Drug

Relationship of an AE or SAE to investigational product is to be determined by the Investigator based on the definitions in Table 7-1.

Table 7-1: Adverse Event Relatedness

Relationship to Study Drug	Definition
Not Related	Unrelated to investigational product
Possibly Related	A clinical event or laboratory abnormality with a reasonable time sequence to administration of investigational product, but which could also be explained by concurrent disease or other drugs or chemicals.
Probably Related	A clinical event or laboratory abnormality with a reasonable time sequence to administration of investigational product, unlikely to be attributable to concurrent disease or other drugs and chemicals and which follows a clinically reasonable response on de-challenge. The association of the clinical event or laboratory abnormality must also have some biologic plausibility, at least on theoretical grounds.

Intensity

The Investigator is to determine the intensity of the AE according to the criteria in Table 7-2.

Table 7-2: Adverse Event Grading

Severity	Definition
Grade 1 (Mild):	Mild; asymptomatic or mild symptoms; clinical or diagnostic observations only; intervention not indicated.
Grade 2 (Moderate):	Moderate; minimal, local or noninvasive intervention indicated; limiting age-appropriate instrumental ADL.
Grade 3 (Severe):	Severe or medically significant but not immediately life-threatening; hospitalization or prolongation of hospitalization indicated; disabling; limiting self-care ADL.
Grade 4 (Life-threatening):	Life-threatening consequences; urgent intervention indicated.
Grade 5 (Death):	Death related to AE.

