7.12.4.2. Follow-Up of Adverse Events

The Investigator must continue to follow all SAEs and non-serious AEs considered to be reasonably or possibly related to study drug either until resolution or the Investigator assesses them as chronic or stable. This follow-up may extend after the end of the study.

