- All TEAE leading to permanent study drug discontinuation by SOC and PT (Statistical Table 14.3.4.5, only produced if more than 5 events)
- All TEAE leading to permanent study discontinuation by SOC and PT (Statistical Table 14.3.4.6, only produced if more than 5 events)

Detailed Tables on TESAEs:

- Any TESAЕ by SOC and PT (Statistical Table 14.3.5.1)
- All possibly or probably related TESAЕs by SOC and PT (Statistical Table 14.3.5.2, only produced if more than 5 events)
- All TESAЕ by SOC, PT and intensity (Statistical Table 14.3.5.3)
- All TESAЕ leading to permanent study drug discontinuation by SOC and PT (Statistical Table 14.3.5.4, only produced if more than 5 events)
- All TESAЕ leading to permanent study discontinuation by SOC and PT (Statistical Table 14.3.5.5, only produced if more than 5 events)
- Death: all causes of mortality and mortality due to respiratory declines (Statistical Table 14.3.5.6)

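### Mortality is a 28-week endpoint, but in subjects who withdraw early, new deaths more than about 4 weeks after the last dose are not systematically captured to Week 28

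*SAP*

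**What the plan says.** **The endpoint.** Protocol 3.2 opens its safety list with "Tolerability/safety will be assessed over the 28-week study period by the following parameters". The list includes all-cause mortality and mortality due to respiratory deterioration. SAP 4.2.1 repeats both.

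**The analysed window.** Protocol 7.12.2 says that "only AEs occurred from the time of first study treatment dose administered to the subject (TEAEs) until last study visit will be analysed". SAP 4.2.1 defines a TEAE as "any adverse event that occurs from the time of first study treatment dose administered to the patient until last study visit". It then states the 28-week period differently: "the analysis will be based on all AEs occurring before first dose of the OLE". SAP 2.3.3 adds that Week 28 is the end-of-study date for all its analyses.

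**Follow-up after withdrawal.** Protocol 7.12.1 enters AEs in the database up to the last study visit. For those who leave early it says "TEAEs will be monitored until, at least, 4 weeks from last study treatment dose or resolution of AE, whichever is earlier". Protocol 5.4 puts the End of Study visit 4 weeks (±3 days) after the last dose. Protocol 7.12.4 limits SAE recording to serious TEAEs. Protocol 7.12.4.2 goes further for events already known: "The Investigator must continue to follow all SAEs and non-serious AEs considered to be reasonably or possibly related to study drug", until they resolve or are judged chronic or stable, if necessary beyond the end of the study.

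**Withdrawal.** Protocol 5.2 lists disease progression among the reasons for which the investigator may withdraw a subject from the study.

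**The output.** SAP 5.2.6.1 places Table 14.3.5.6, "Death: all causes of mortality and mortality due to respiratory declines", under the heading for treatment-emergent SAE tables. The table list in SAP 9.1 titles it simply as deaths.

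**The concern.** An endpoint stated over 28 weeks needs survival status over 28 weeks for everyone in the denominator. Here follow-up is tied to the last dose. A subject who stops early has a last visit well before Week 28, and nothing in the schedule of events or the disposition table of SAP 5.2.2 asks whether that subject is alive at Week 28. The SAP gives no censoring rule, number at risk or category for unknown status, so a simple percentage of the safety set would in effect count such a subject as a survivor.

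Subjects withdrawn for progression are plausibly at higher risk of death than those who stay. If such withdrawals are unequal between arms, the mortality comparison is distorted as well as understated. The arms are small: one missed death is 1/39 = 2.6 percentage points on placebo and 1/78 = 1.3 on PRM-151.

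This is separate from the missing Week 28 FVC. Vital status can often be learned when spirometry cannot be obtained.

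**Working it through.** The documents state no expected mortality, so there is no plan figure to reproduce for this point. The sample size concerns FVC only and is unaffected. The check has three steps.

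**1. Where required follow-up ends.** Take it as last dose + 4 weeks (Protocol 5.4 and 7.12.1). Gap = 28 − (last dose week + 4).

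| Last dose (week) | 0 | 4 | 8 | 12 | 16 | 20 | 24 |
|---|---|---|---|---|---|---|---|
| Follow-up required to (week) | 4 | 8 | 12 | 16 | 20 | 24 | 28 |
| Weeks left to Week 28 | 24 | 20 | 16 | 12 | 8 | 4 | 0 |

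The gap is zero for anyone dosed at Week 24. For example, suppose a subject is last dosed at Week 8 and seen at Week 12, has a new acute exacerbation at Week 18 and dies at Week 20. The death lies inside the endpoint period, but no required contact would find it. Open-SAE follow-up does not apply, because the event began after the last visit.

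**2. End points given for the same period.**

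- Last study visit: Protocol 7.12.2 and SAP 4.2.1.
- At least 4 weeks after the last dose, or resolution if earlier: Protocol 7.12.1. One clause sets both a floor and an earlier stop.
- First open-label dose: SAP 4.2.1. This sets no limit for someone who never enters the extension.
- Resolution, or chronic or stable: Protocol 7.12.4.2, for SAEs already open.

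These do not coincide for a subject who withdraws early, and the SAP does not say which of them bounds Table 14.3.5.6.

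**3. Illustrative size.** Inputs:

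- 117 subjects (Protocol 8.1).
- Median survival of 3 years after diagnosis (Protocol 1.1), read as a constant hazard: ln 2 / (3 × 52.18 weeks) = 0.00443 per week.
- Assumption: last doses of early withdrawals are spread evenly over Weeks 0 to 20, so the mean gap is (24+20+16+12+8+4)/6 = 14 weeks.
- Assumption: 5%, 15% or 25% withdraw early. The documents give no rate. The 15% in Protocol 8.1 is non-evaluability, which is not the same thing.
- Assumption: SAE follow-up finds none of these deaths.

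Missed deaths = 117 × withdrawal rate × mean over the six gaps of [1 − exp(−hazard × gap)]. At the base hazard that mean is about 0.060, so for 15%: 117 × 0.15 × 0.060 = 17.55 × 0.060 ≈ 1.05.

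| Early withdrawal | Subjects | Half the hazard | 3-year-median hazard | Twice the hazard |
|---|---|---|---|---|
| 5% | 5.85 | 0.18 | 0.35 | 0.67 |
| 15% | 17.55 | 0.53 | 1.05 | 2.02 |
| 25% | 29.25 | 0.89 | 1.75 | 3.36 |

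For scale, the base hazard gives 28-week mortality of 1 − exp(−0.00443 × 28) = 11.7%, or about 13.6 deaths in 117. The middle column is then 0.35/13.6 = 3% to 1.75/13.6 = 13% of expected deaths.

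**The case against.** A reader might infer that deaths are captured only to the last visit and that any later death is left out of the table. The documents do not support that.

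- An SAE open at withdrawal can be followed to a fatal outcome under Protocol 7.12.4.2, and the 4 weeks in Protocol 7.12.1 is worded as a minimum.
- SAP 4.2.1 lists mortality separately from TEAEs and also bounds the analysis by the first open-label dose, which imposes no last-visit cut-off on subjects who never enter the extension.
- Table 14.3.5.6 carries no treatment-emergent label in SAP 9.1, unlike most of its neighbours. SAP 5.2.6.1 also has a deaths row in the AE summary and a separate listing of deaths. Restriction to the TEAE window is possible but not shown.
- Protocol 7.12.4.3 requires investigators to report deaths to the ethics committee without a stated time limit.

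These points narrow the claim but do not close the gap. Open-SAE follow-up does not reach a new event. An analysis cut-off cannot include deaths that nobody has to collect. A report to an ethics committee is not a database entry.

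The size can also be challenged, and that criticism stands. Under Protocol 8.4 and 8.5.1.1, a subject with one post-baseline FVC stays evaluable through carry-forward, so non-evaluability is a poor proxy for withdrawal. Survival after diagnosis may overstate the hazard in subjects required to have a life expectancy of at least 9 months and FVC of at least 50% predicted. Doubling the hazard is an assumption without a source.

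Finally, this is a pilot in which mortality is tabulated without a planned test. With a half-life of at most 44 hours (Protocol 6.8), 4 weeks is about 672/44 = 15 half-lives, a defensible window for drug-related events. But the stated endpoint is mortality over 28 weeks, not mortality within an exposure window.

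**Conclusion.** The point holds in a limited form. For subjects who withdraw early, new deaths arising more than about 4 weeks after the last dose are not systematically captured to Week 28, although mortality is an endpoint over that period. Because progression is a permitted withdrawal reason, the loss may be informative. Separately, the differing end points and the unclear scope of the death table need to be settled.

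The likely number is small: about 0.35 to 1.75 missed deaths for 5% to 25% early withdrawal, and about 0.7 to 3.4 at twice the hazard. Those figures rest on an assumed withdrawal rate, evenly spread stopping times, a constant hazard that may be too high, and no deaths found through SAE follow-up. They show scale and are not a forecast.

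A reader might go further and conclude that the mortality comparison is biased. The documents show only that it could be, since nothing in them indicates how withdrawals will fall between arms. The primary FVC analysis is a separate matter.

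**What to change.** 1. Record vital status, with date and cause of death where applicable, at nominal Week 28 for every treated subject, by phone or chart review and subject to consent.
2. Define mortality in the SAP apart from TEAEs: all deaths from first dose to Week 28 (Day 196, plus the visit window) or first open-label dose, whichever comes first. Report by arm with number at risk and number of unknown status, and show deaths inside the TEAE window as a subset. State that this definition governs Table 14.3.5.6.
3. Reconcile Protocol 7.12.1, 7.12.2 and 7.12.4.2 with SAP 4.2.1 so that one follow-up end point applies.

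Cost: a protocol amendment needing ethics approval (Protocol 9.4) across the 18 sites in 8 countries of SAP 5.3.4, one eCRF item, one revised table definition, and one contact per early withdrawal (about 6 to 29 subjects over the assumed 5% to 25% range). Subjects who withdraw all consent will remain unknown and should be shown as such.
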